- 8. Have a history of a structural cardiac abnormality, valvular cardiac disease, cardiomyopathy, 228 serious heart rhythm abnormality, coronary artery disease, congestive heart failure, stroke, or other 229 serious cardiovascular problem. 230
- 9. Have an ECG with significant arrhythmias or conduction abnormalities, which in the opinion of 231 the physician investigator preclude study participation. 232
- 10. Have clinically relevant abnormal laboratory results. 233
- 11. Participants requiring treatment with any drug which might interact adversely with or obscure the 234
- action of the study medication. This includes anti-obesity drugs, psychostimulants, modafinil or 236 235 armodafinil, and topiramate or zonisamide. Participants receiving metformin at a stable dose for ≥ 237 3 months can be included.
- 12. Participants receiving GLP-1 based therapies, sodium-glucose co-transporter 2 inhibitors 238 (SGLT2s), thiazolidinediones, sulfonylureas, or insulin. 239
- 13. Participants with a personal or family history of medullary thyroid carcinoma or Multiple 240 Endocrine Neoplasia syndrome type 2. 241
- 14. Participants who have received any investigational medication within three months prior to 242 randomization. 243
- 244 15. Participants previously screen-failed or randomised to participate in this trial.
- 16. Participants who have a known or suspected allergy to liraglutide 3.0 mg sc injection, its 245 constituents, or related products. 246
- 17. Participants with a urine drug screen positive for a drug that, in the opinion of the investigator, is 247 being abused. 248
- 18. Participants with a past medical history of pancreatitis. 249
- 19. Participants who had received any investigational drug within 3 months prior to this trial. 250
- 20. Participants who require bariatric surgery or are anticipated to require it during the course of the 251 trial. If such surgery becomes warranted during the study, such patients will be excluded from the 252 primary endpoint analysis. 253
- 254
- 255
- 256 257

258 Withdrawal Criteria:

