The primary efficacy measure will be the percent change in body weight from Baseline to Week 40/Early Termination. Weight will be measured in kg and obtained on the same scale, zeroed at each use, and with the subject in light clothing and no shoes. Secondary efficacy variables will be proportion of patients who have $\geq 5\%$ reduction in body weight, and changes in body weight (kg), BMI, waist circumference, and measures of metabolic variables (fasting lipids and glucose, and HgA₁c).

439

440 Assessments for Safety

The investigator will conduct and record a medical history at the Screening Visit, including a medication
 history and all clinically relevant information in conjunction with a Physical Examination. Any

- history and all clinically relevant information in conjunction with a Physical Examination
 abnormalities in the review of systems and exam will be noted in the source documents.
- 444

The following assessments will be used to assess safety at each visit: vital signs, taken after the participant is rested and seated for 5 minutes, mental status examination, YMRS, MADRS, CGI-BP-Severity and -Improvement Scales, C-SSRS, urine pregnancy test, concomitant medication form, adverse

- events, drug interaction form, and study drug accountability. All adverse events will be evaluated as
 potential drug interactions for those medications used to treat BP (mood stabilizers, antipsychotics,
- 450 antidepressants, anxiolytics, and sedative-hypnotics) with the drug interaction form. A drug interaction is
- defined as an AE that is possibly due to an interaction between study drug and a BP medication a subject
- 452 is receiving.
- 453

The YMRS (56) is a widely used, validated, and reliable clinician-administrated instrument that assesses the severity of the symptoms of mania. It consists of 11 items rated on a scale of 0 to 4 (items 1-4, 7, 10, and 11) or 0 to 8 (items 5, 6, 8, and 9) (total score range 0 to 60), with 0 being the absence of symptoms and higher scores representing greater severity of manic symptoms. The total thus ranges from 0 (no symptoms) to 60 (extremely severe symptoms). A mild level of symptoms corresponds to a score of \leq 12.

- 460 The MADRS (57) is a widely used, validated, and reliable clinician-administered measure of depressive
 461 symptoms. It consists of 10 items, with each item yielding a score of 0 to 6 (total score range 0 to 60). 462

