The power analysis for this study uses a two-sample t-test on the mean weight change from baseline to 510 week 40 (or endpoint for patients who discontinue prematurely) in the two treatment groups in the

- 511
- modified intent-to-treatment (ITT) sample. This sample will consist of all study participants who: 1) were 512 randomized, 2) received at least one study medication dosage, and 3) had at least one post-baseline 513
- efficacy assessment. We expect a 5% attrition rate from baseline to week 1. We therefore expect the
- 514 proposed sample size of 60 to give an ITT sample of 56. Using this ITT sample size, along with a
- 515 significance level of 0.05 and power of 0.80, we will be able to detect effect sizes as small as 0.76. 516
- 517
- This effect size corresponds to a 4.5 kg greater weight reduction in the liraglutide group vs. the placebo 518
- group. The 4.5 kg reduction was calculated (0.76 x 6.0) using an expected standard deviation (SD) of 6.0 519
- kg based on Wadden et al. (SD=7.0 at 56 weeks) and Astrup et al. (SD=5.6 for power analysis). This is a 520
- clinically meaningful difference, especially in this population, where many patients are taking 521
- 522 antipsychotics, which are associated with weight gain. We expect our primary analysis (longitudinal
- mixed model) to have more power due to the repeated visit data for each subject (60 subjects x 16 524 523
- treatment period visits = 960 maximum number of observations).

525 526

- **Statistical Methods** Chi-square, Fisher's Exact, Wilcoxon rank sum or two-sample t-tests will be used to examine statistical 527
- differences between the placebo and drug condition on baseline characteristics and categorical outcome 528
- measures. The primary analyses will be longitudinal data analyses (LDA) using PROC MIXED (SAS, 529
- Cary N.C. U.S.A.). LDA will model the mean change in the primary and secondary outcome measures, 530 over the treatment period, between the placebo and drug condition. LDA is advantageous because it 532
- 531 accounts for change over time, includes all data points, and adjusts for the correlation resulting from 533 repeated measures. These LDA models will include variables for treatment, time, and treatment x time

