- interaction. The statistical test for the interaction term will be the measure of a treatment effect. The 535 534 interaction term will test if the slopes of the regression lines for the liraglutide and placebo groups are 536 different. A group difference (Drug [week 40-week 0] – Placebo [week 40-week 0]) will be reported 537 which corresponds to the interaction term. For the primary outcome of percent change in body weight,
- only post-baseline data will be used in the LDA model and the difference between treatments at week 40 538
- will be reported. These mixed models will allow for random coefficients (intercept and time variable), as 539
- 540 well as an appropriate correlation structure for the error terms to account for within-subject
- correlation. The best model will be chosen using the Akaike Information Criterion-corrected 541
- (AICc). The distribution of the outcome measures will be checked for normality, and transformations will 542 be used when necessary. Also, a transformation on the time variable will be considered to optimize the 544 543
- assumed linear relationship.
- 545

- 546 Additionally, secondary endpoint analyses will be performed on all outcome measures. Using the last
- 547 observation carried forward (LOCF), baseline to endpoint change scores will be computed for each 548 measure and two-sample t-tests or Wilcoxon rank sum tests will be used to compare these changes 549 between the treatment groups.
- 550

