Waist circumference		x	X	x	x	x	x	x	x	x	x	x	x	x	x	x	x	x	
Clinical laboratory tests ^b	x							x				x						x	
12-lead ECG	X							X				X						x	
Serum pregnancy test	X																		
Urine Pregnancy test		x	X	x	X	x	x	x	x	x	x	x	x	x	x	x	x	x	x
Urine drug screen	x																		
YMRS	x	x	x	x	x	x	x	x	x	x	x	X	x	x	x	x	x	x	x
MADRS	X	x	x	x	x	x	x	x	x	x	x	x	x	x	x	x	x	x	x
CGI-BP-S	X	x	x	X	X	X	x	X	X	X	X	x	x	x	x	x	x	x	x

[name]

July 11,2017

CGI-BP-I			X	x	x	x	x	X	x	X	x	X	x	x	x	X	X	X	X
Lifestyle counseling		x				x		x		x		x	x	x	x	x	x		
TFEQ		x				x		x		x		x	x	x	x	x	X	X	
BES		x				x		x		x		x	x	x	x	x	X	X	
C-SSRS- Baseline Version	X																		
C-SSRS- Since Last Visit Version		X	X	x	X	x	x	X	x	x	x	x	x	x	x	x	X	X	X
Suitability to remain in study	X	X	x	x	x	x	x	X	X	X	x	X	X	x	X	X	X	x	
Investigational product dispensed		X	x	x	x	x	x	X	x	X	x	x	X		X	X			
Investigational product returned			x	x	X	x	x	X	x	X	x	X	X		X	X		X	
Compliance assessed			x	x	x	x	x	X	x	X	x	X	x	x	x	x	x	x	
Concomitant medications	X	X	X	x	X	x	x	X	x	X	x	x	x	x	x	x	X	X	x
Adverse events	X	x	x	x	X	x	x	x	x	X	x	x	x	x	x	x	X	x	X
Drug interaction form	X	X	x	x	x	x	x	x	x	x	x	x	x	x	x	x	X	x	x
Termination record																			X

^aWeight (using a calibrated scale) and height to be measured without shoes. ^bLaboratory samples will be obtained when the subject is fasting and will include CBC with diff, Metabolic profile, lipids, HgA_{1c}. Participants must fast for 12 hours prior to laboratory samples being collected.

ubject #:	Date:
 Was there any in psychiatric media 	formation suggesting the subject had an interaction between liraglutide and a ation?
□ Yes	□ No
If YES, provide	a complete description of the putative interaction.
2. Please list all psy	ychiatric medications involved in this interaction.
3. Was any action t	taken to manage the interaction?
\Box Yes	\Box No
If YES, please ex	xplain:
4. Outcome of inter	raction:

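### Exclusion item 20 removes randomised participants from the primary analysis on an undefined judgement about bariatric surgery, and the rest of the plan does not reconcile it (minor)

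*Combined protocol and SAP*

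**What the plan says.** Item 20 of the Exclusion Criteria opens as an eligibility rule: "Participants who require bariatric surgery or are anticipated to require it during the course of the" trial are not to be enrolled. Its second sentence concerns people already in the study: "If such surgery becomes warranted during the study, such patients will be excluded from the" primary endpoint analysis.

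The modified ITT sample is defined under Sample Size Calculation by three conditions: "This sample will consist of all study participants who: 1) were" "randomized, 2) received at least one study medication dosage, and 3) had at least one post-baseline" efficacy assessment. Surgery is not mentioned.

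Elsewhere the plan keeps people who stop early. Under Assessments for Efficacy, "The primary efficacy measure will be the percent change in body weight from Baseline to Week 40/Early Termination". The power calculation compares change to "week 40 (or endpoint for patients who discontinue prematurely) in the two treatment groups in the" modified ITT sample. The secondary analyses are change scores by last "observation carried forward (LOCF), baseline to endpoint change scores will be computed for each" measure.

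The Withdrawal Criteria list pregnancy, psychiatric worsening, suicidality and non-compliance, but not surgery. Statistical Methods covers the mixed model, LOCF, intermittent missing visits and the safety population without referring to item 20. Subject Replacement allows no replacement after Baseline.

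**The concern.** Anyone who could be removed from the primary endpoint analysis has already been randomised, so the sentence is a post-randomisation exclusion, placed where an analyst working from the statistical section may not see it. Four things are left open:

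- what makes surgery *warranted*, who decides, and when;
- whether surgery must actually be done;
- whether all of the participant's weights go, or only later ones (removal of the whole participant is the natural reading);
- whether the exclusion also applies to the LOCF analyses.

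The primary outcome is percent change in weight. A judgement that weight-loss surgery has become warranted is plausibly related to poor weight response, although the documents do not establish this. If it is related, the rule selects on the outcome. Removing poor responders from the liraglutide arm would flatter liraglutide, and removing them from placebo would count against it.

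**Working it through.** **1. The texts side by side.** Take a randomised, dosed participant with several post-baseline weights for whom surgery is judged warranted at some visit.

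| Place | Treatment of this participant |
|---|---|
| Exclusion item 20 | Out of the primary endpoint analysis |
| Sample Size Calculation, modified ITT | Meets all three conditions |
| Withdrawal Criteria | Surgery not listed, so the participant may stay in the study |
| Statistical Methods | Silent; the stated missing-data rule covers intermittent missed visits only |

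The analysis set therefore depends on which section is followed.

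**2. The plan's own figure.** Inputs from Sample Size Calculation: modified ITT 56 (28 per arm at 1:1), power 0.80, effect size 0.76, SD 6.0 kg, significance level 0.05 (two-sided under Statistical Methods). A two-sample t-test with the noncentral t distribution gives a detectable effect of 0.762 and power 0.798 at 0.76, so the stated figure reproduces. In kg, 0.76 × 6.0 = 4.56, which the plan gives as 4.5.

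**3. Standard error of the difference.** 6.0 × √(2/28) = 1.60 kg.

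**4. Possible shift.** The documents give no surgery rate and no SD for percent change, so this is an illustration in kg. Assume *k* participants are removed from one arm of 28, each having done *D* kg worse than the full arm mean. The remaining mean moves by *kD*/(28 − *k*).

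| *D* (assumed) | *k* = 1 | *k* = 2 |
|---|---|---|
| 0 kg | 0 | 0 |
| 3 kg | 3/27 = 0.11 kg | 6/26 = 0.23 kg |
| 6 kg | 6/27 = 0.22 kg | 12/26 = 0.46 kg |
| 9 kg | 9/27 = 0.33 kg | 18/26 = 0.69 kg |

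For *D* from 3 to 9 kg the range is 0.11/4.5 = 2.5% to 0.69/4.5 = 15% of the planned difference, or 0.11/1.60 = 0.07 to 0.69/1.60 = 0.43 standard errors. With no cases the shift is zero.

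**5. Power at effect size 0.76.** 28 + 28: 0.798. 27 + 28: 0.790. 26 + 28: 0.782.

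**6. Limits of the illustration.** The comparator is the arm mean with every participant's endpoint observed. The primary analysis is a longitudinal model of percent change, and the fix below would itself leave out post-surgery values, so the table does not measure what the fix would gain. Removals in both arms would partly cancel.

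**The case against.** The sentence has a sensible aim. If post-surgery weights were kept with no rule, weight lost through an operation would be credited to the assigned arm. The trial is double-blind with identical pens, and one staff member holds the allocation, so the judgement could hardly be made with an eye to the arm. The same item bars anyone already expected to need surgery, so in 60 participants over 40 weeks there may be no case at all. Defining the trigger and adding a cross-reference would cure the ambiguity.

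Most of this stands, and it limits the weight of the point. It does not make the rule sound. Blinding does not stop selection on weight response, and surgical weight loss can be handled without discarding what was measured before surgery. A better-defined trigger would still be a post-randomisation exclusion.

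Three stronger readings are tempting but are not supported:

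- **A flat contradiction.** A reader might infer that the modified ITT definition and item 20 directly conflict. That sample is defined only under Sample Size Calculation, and no population is named for the mixed model. The passages are unreconciled, which is a lesser fault.
- **Material inflation of type I error.** If the one or two worst of 28 in a single arm were removed, the shift would be about 0.45 or 0.83 kg and the two-sided error would rise from 0.050 to 0.066 or 0.093. Nothing in the documents indicates that the removed participants would be the extremes of one arm.
- **A defined exit route.** Table 1 has a row labelled "Suitability to remain in study", from which a reader might infer that these participants leave through an early termination visit. Nothing links that row to surgery.

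**Conclusion.** The point holds as a minor one. Item 20 lets an undefined judgement, plausibly tied to the outcome, change the primary analysis set after randomisation, and no other section repeats, limits or reconciles it. The direction of any bias cannot be predicted, and the documents do not support the inference that the rule favours liraglutide.

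The likely size is nil or small. Under the assumed values (one or two removals, all in one arm, 3 to 9 kg worse than the arm mean, whole participant removed), the difference moves by about 0.1 to 0.7 kg against a planned 4.5 kg. Power falls by at most 0.798 − 0.782 = 0.016. The case for changing the text rests on the principle and on the low cost of the change, not on an expected large effect.

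**What to change.** - Delete the analysis-exclusion sentence from item 20 and leave the entry criterion as it is.
- State under Statistical Methods that the primary mixed-model analysis uses the modified ITT sample and keeps these participants' data up to the date of any surgery actually performed. A judgement that surgery is warranted would then have no effect on the analysis set.
- Prespecify that values after surgery are not used in the primary analysis, and apply the same rule to the secondary weight and metabolic endpoints and to the LOCF analyses.
- Report the analysis that excludes these participants entirely only as a sensitivity analysis, with counts by arm.

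The cost is a few sentences, one recorded date and one extra sensitivity analysis, with no new visits or measurements. The statistical price is reliance on missing at random after surgery, which should be stated because the plan's present assumption covers intermittent missed visits only. If no case arises, the results are unchanged.
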